6.3.4. Safety Analysis Population

The safety analysis population will consist of all subjects with recorded receipt of any amount of study product. The analyses on the safety analysis population will be performed per treatment actually received.

6.4. Covariates and Subgroups

Subjects will be recruited from multiple clinical sites, but randomization will not be stratified by site. Randomization will use a total of 12 strata, with stratification by 1) age group (<24 months vs. 24-71 months), 2) initially prescribed antibiotic (amoxicillin vs. amoxicillin-clavulanate vs. cefdinir), and 3) treatment site (emergency department vs. outpatient clinic/urgent care facility).

6.5. Missing Data

While all efforts will be made to minimize missing data, some missing data is expected. Whenever possible, subjects terminating from the study early will be given an early termination visit during which the available components of the DOOR and related measures can be recorded. The primary analysis will use multiple imputation with linear models to impute values using available information (treatment, randomization strata variables, and available visit information), assuming a missing at random (MAR) model. Secondary analyses will further examine the robustness of this analysis, including a “worst case analysis” in which all imputations of missing

data will be the worst case (result in the lowest possible DOOR given available information) for subjects in the 5-day arm and best case for subjects in the 10-day arm. Day 1 in this study is defined as the date of first receipt of study product. If a subject has no record of study product administration or did not receive a first dose of study product, but has other post-randomization data, Day 1 will be imputed as the date 5 days after the date of first receipt of initial antibiotic.

In some cases, a subject may have DOOR defined despite missing some of its components, in which case the subject will be eligible for inclusion into the CC and ATP analysis populations. In analyses of the components of the DOOR using the CC and ATP analysis populations, data will be analyzed as available and missing data will not be imputed.

The study includes several composite variables with rules for assignment, missingness, and imputation described below.

6.5.1. Adequate Clinical Response to OAV#1 or OAV#2

Subjects that have no record of receipt of at least one dose of study product will have adequate clinical response and its components considered missing at both OAV#1 and OAV#2. Otherwise, if a subject dies at any point during subject participation in the study, the subject will be considered as not having adequate clinical response at OAV#1 or OAV#2. Otherwise, if a subject does not have OAV#1 then ACR and its components are missing for OAV#1 and if a subject does not have OAV#2 then ACR and its components are missing for OAV#2.

Several variables are used to define the Adequate Clinical Response:

- MAVABRX: Was the subject prescribed or did the subject receive an additional antibiotic treatment at this visit? (Yes/No)
 - o MAVABCP: If Yes, was the antibiotic given for pneumonia or treatment for a complication of pneumonia? (Yes/No)
- MAVPLEUR: Drainage of pleural fluid as treatment for pneumonia or a complication of pneumonia? (Yes/No)
- MAVCHTB: Placement of a chest tube as treatment for pneumonia or a complication of pneumonia? (Yes/No)
- MAVVIDEO: Video assisted thoracoscopic surgery as treatment for pneumonia or a complication of pneumonia? (Yes/No)
- MAVTHOR: Thoracotomy procedure as treatment for pneumonia or a complication of pneumonia? (Yes/No)
- MAVSURG: Any other surgical procedure as treatment for pneumonia or a complication of pneumonia? (Yes/No)
- MAVHOSP: Was the subject hospitalized at this visit? (Yes/No)
 - o MAVHPPN: If Yes, was the hospitalization for the treatment of pneumonia or pneumonia complications? (Yes/No)

If a subject has OAV#1 and did not have a medically attended visit (MAV) from Day 1 to Day 5, inclusive, then the subject had adequate clinical response for OAV#1. If the subject had a MAV from Day 1 to Day 5 for which MAVABRX and MAVABCP were both YES (receipt of a non-

study systemic antibiotic for pneumonia), or for which MAVPLEUR, MAVCHTB, MAVVIDEO, MAVTHOR, or MAVSURG were YES (treatment for a complication of pneumonia, including drainage of pleural fluid, placement of a chest tube, video assisted thoracoscopic surgery, or thoracotomy procedures), then the subject did not have adequate clinical response at OAV#1. If the subject had a MAV from Day 1 to Day 5 for which MAVHOSP and MAVHPPN were both YES (subject was hospitalized for the treatment of pneumonia or pneumonia complications), then the subject did not have adequate clinical response at OAV#1. Otherwise, if the subject had a MAV from Day 1 to Day 5 and either MAVABRX was missing, MAVABRX was YES and MAVABCP was missing, or any of MAVPLEUR, MAVCHTB, MAVVIDEO, MAVTHOR, or MAVSURG were missing, then adequate clinical response at OAV#1 is missing. Otherwise, if a subject has one or more MAVs from Day 1 to Day 5, with no MAV indicating receipt of a non-study systemic antibiotic for pneumonia or treatment for a complication of pneumonia, including drainage of pleural fluid, placement of a chest tube, video assisted thoracoscopic surgery, or thoracotomy procedures and no hospitalization for treatment of pneumonia or pneumonia complications and no MAV missing data as described, then the subject has adequate clinical response at OAV#1. Note that for determining whether the medical treatment or hospitalization falls within the period of Day 1 to Day 5, the date of the initial MAV will be used (MAVVISDT), rather than specific dates of surgery or hospitalization entered on the MAV form.

If a subject has OAV#2 and did not have a medically attended visit (MAV) from Day 1 to Day 18, inclusive, then the subject had adequate clinical response for OAV#2. If the subject had a MAV from Day 1 to Day 18 for which MAVABRX and MAVABCP were both YES (receipt of a non-study systemic antibiotic for pneumonia), or for which MAVPLEUR, MAVCHTB, MAVVIDEO, MAVTHOR, or MAVSURG were YES (treatment for a complication of pneumonia, including drainage of pleural fluid, placement of a chest tube, video assisted thoracoscopic surgery, or thoracotomy procedures), then the subject did not have adequate clinical response at OAV#2. If the subject had a MAV from Day 1 to Day 18 for which MAVHOSP and MAVHPPN were both YES (subject was hospitalized for the treatment of pneumonia or pneumonia complications), then the subject did not have adequate clinical response at OAV#2. Otherwise, if the subject had a MAV from Day 1 to Day 18 and either MAVABRX was missing, MAVABRX was YES and MAVABCP was missing, or any of MAVPLEUR, MAVCHTB, MAVVIDEO, MAVTHOR, or MAVSURG were missing, then adequate clinical response at OAV#2 is missing. Otherwise, if a subject has one or more MAVs from Day 1 to Day 18, with no MAV indicating receipt of a non-study systemic antibiotic for pneumonia or treatment for a complication of pneumonia, including drainage of pleural fluid, placement of a chest tube, video assisted thoracoscopic surgery, or thoracotomy procedures and no hospitalization for treatment of pneumonia or pneumonia complications and no MAV missing data as described, then the subject has adequate clinical response at OAV#2. Note that for determining whether the medical treatment or hospitalization falls within the period of Day 1 to Day 18, the date of the initial MAV will be used (MAVVISDT), rather than specific dates of surgery or hospitalization entered on the MAV form.

The below pseudocode summarizes the logic for defining ACR at OAV#1.

```
if no recorded receipt of study product then ACR_OAV1=missing  
else if death then ACR_OAV1=NO
```

```

else if subject does not have OAV#1 then ACR_OAV1=missing
else if subject has no MAV from Day 1 to Day 5 then ACR_OAV1=YES
else if subject has one or more MAVs from Day 1 to Day 5 with
    (MAVABRX=YES and MAVABCP=YES) or
    MAVPLEUR=YES or
    MAVCHTB=YES or
    MAVVIDEO=YES or
    MAVTHOR=YES or
    MAVSURG=YES or
    (MAVHOSP=YES and MAVHPPN=YES)
    then ACR_OAV1=NO
else if subject has MAV from Day 1 to Day 5 with
    MAVABRX=missing or
    (MAVABRX=YES and MAVABCP=missing) or
    MAVPLEUR= missing or
    MAVCHTB= missing or
    MAVVIDEO= missing or
    MAVTHOR= missing or
    MAVSURG= missing

then ACR_OAV1=missing
else ACR_OAV1=YES

```

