6.5.5. Ordinal Clinical Response at OAV#1 or OAV#2

If the subject died at any point of study participation, then OCR at OAV#1 will be 8.

Else if the subject has missing ACR at OAV#1 then OCR at OAV#1 will be missing.

Else if the subject did not have ACR at OAV#1 and was hospitalized from Day 1 to Day 5 then OCR at OAV#1 will be 7.

Else if the subject did not have ACR at OAV#1 and was not hospitalized from Day 1 to Day 5 then OCR at OAV#1 will be 6.

Else if the subject has missing resolution of symptoms at OAV#1 then OCR at OAV#1 will be missing.

Else if the subject did not have resolution of symptoms at OAV#1 then OCR at OAV#1 will be 5.

Else if the subject has missing most severe solicited event at OAV#1 then OCR at OAV#1 will be missing.

Else if the subject had a most severe solicited event of grade 3 at OAV#1 then OCR at OAV#1 will be 4.

Else if the subject had a most severe solicited event of grade 2 at OAV#1 then OCR at OAV#1 will be 3.

Else if the subject had a most severe solicited event of grade 1 at OAV#1 then OCR at OAV#1 will be 2.

Else OCR at OAV#1 will be 1.

If the subject died at any point of study participation, then OCR at OAV#2 will be 8.

Else if the subject has missing ACR at OAV#2 then OCR at OAV#2 will be missing.

Else if the subject did not have ACR at OAV#2 and was hospitalized from Day 1 to Day 18 then OCR at OAV#2 will be 7.

Else if the subject did not have ACR at OAV#2 and was not hospitalized from Day 1 to Day 18 then OCR at OAV#2 will be 6.

Else if the subject has missing resolution of symptoms at OAV#2 then OCR at OAV#2 will be missing.

Else if the subject did not have resolution of symptoms at OAV#2 then OCR at OAV#2 will be 5.

Else if the subject has missing most severe solicited event at OAV#2 then OCR at OAV#2 will be missing.

Else if the subject had a most severe solicited event of grade 3 at OAV#2 then OCR at OAV#2 will be 4.

Else if the subject had a most severe solicited event of grade 2 at OAV#2 then OCR at OAV#2 will be 3.

Else if the subject had a most severe solicited event of grade 1 at OAV#2 then OCR at OAV#2 will be 2.

Else OCR at OAV#2 will be 1.

Note that in some cases OCR can be defined even if some components are missing. For instance, if a subject had record of receipt of study product and did not have adequate clinical response at OAV#1, OCR at OAV#1 would still be defined even if most severe solicited event at OAV#1 was missing.

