6.5.6. Number of Days of Antibiotic Use at OAV#1 or OAV#2

It will be assumed that all subjects have precisely five days of antibiotic use with the initial antibiotic prior to Day 1 (the day of the first dose of study product). Analysis involving comparisons of the number of days of antibiotic use will consider antibiotic use from Day 1 onwards. The number of days of antibiotic use is defined as the actual number of days of antibiotic use (any amount of study product that is not placebo, or any amount of other systemic antibiotic) from Day 1 to Day 5, inclusive, for OAV#1 and from Day 1 to Day 18 for OAV#2. For subjects that received placebo as study product, it is counted as the number of days of systemic antibiotic as determined solely from the concomitant medication form. For subjects that receive actual antibiotic as study product, it is counted as the number of days that the subject received any amount of either study product or a non-study systemic antibiotic, as determined

from the concomitant medication form. Note that missed doses of study product do not necessarily lower the number of days of antibiotic use as long as a separate dose of antibiotic (study product antibiotic or concomitant medication antibiotic) was received on that day. Extra doses of study product beyond the protocol specification of 10 doses count as normal toward the number of days of antibiotic use. The number of days of antibiotic use is missing (at both OAV#1 and OAV#2) if the product administration record was not completed / on record for the subject and the subject did not have antibiotic use during the study period recorded as a concomitant medication. If a subject does not have an OAV#1 or OAV#2, then number of days of antibiotic use at OAV#1 is missing. If a subject does not have an OAV#2, then number of days of antibiotic use at OAV#2 is missing. As exceptions, subjects that were hospitalized due to pneumonia or a complication of pneumonia or the died during the study period will have number of days of antibiotic use at OAV#1 or OAV#2 as 5 if randomized to the standard course or as 0 if randomized to short course if the number of days of antibiotic use at OAV#1 or OAV#2 is missing as defined above.

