The number of days of antibiotic use at the time of analysis will be determined from the product administration records and concomitant medication records only. Data management activities and site queries (outside the scope of this document) prior to data lock will ensure concomitant medication records are as complete as possible and consistent with other records (i.e., AEs and medically attended visit records in the clinical database). The number of days of antibiotic use for a concomitant medication will be calculated as the medication end date minus the medication start date plus one day. Days will not be double counted if multiple systemic antibiotics (including antibiotic as study product) are taken on the same day. Systemic antibiotic use will not be counted for days that fall outside of the range being considered (Days 1 to Day 5, or Day 1 to Day 18).

If there is a start date but not an end date for a concomitant medication in the clinical database, then the end date for analysis will be imputed as follows. If the subject completed the study, then the end date for analysis will be reported as the protocol completion date. If the subject terminated early from the protocol and there is at least one other record for the same antibiotic in the concomitant medications records with start and end date known (record may belong to any subject), the end date of treatment for that antibiotic will be imputed by adding the mean observed number of days of treatment rounded up to the nearest integer for that antibiotic (minus 1). If no such records exist for the antibiotic and the subject terminated early, the end date of treatment for that antibiotic will be imputed by adding to the start date the mean observed number of days of treatment rounded up to the nearest integer for all systemic antibiotics in the concomitant medication records (minus 1).

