6.5.7. Desirability of Outcome Ranking (DOOR) at OAV#1 or OAV#2

DOOR at OAV#1 is defined by ranking all subjects (pooling together both treatment arms) according to OCR at OAV#1 (lower is better) and using the number of days of antibiotic use at OAV#1 (lower is better) as a tie-breaker for comparing the ranking of two subjects with the same OCR. DOOR at OAV#2 is defined by ranking all subjects (pooling together both treatment arms) according to OCR at OAV#2 (lower is better) and using the number of days of antibiotic use at OAV#2 (lower is better) as a tie-breaker for comparing the ranking of two subjects with the same OCR. DOOR at OAV#1 or at OAV#2 is missing only if OCR or number of days of antibiotic use is missing for the respective OAV.

The ranking algorithm for DOOR is implemented as follows. A score variable is created that adds the number of days of antibiotic use (as defined in Section 6.5.6) divided by 100 to the OCR. Subjects are then ranked (DOOR) by the score, with the highest rank going to the subject with the lowest score, and the lowest rank going to the subject with the highest score. Tied scores result in a DOOR equal to the mean of the tied ranks. The algorithm is exemplified below using a simple scenario with 4 subjects.

Suppose Subject A has an OCR of 1 and 5 days of antibiotic use in the study period (score=1.05), Subject B has an OCR of 1 and 0 days of antibiotic use (score=1.00), Subject C has an OCR of 2 and 0 days of antibiotic use (score=2.00), and Subject D has an OCR of 1 and 5 days of antibiotic use (score=1.05). Because Subject B has the lowest score, Subject B is given DOOR=1 (the highest rank). Because Subject A and Subject D tie for the next lowest score, they both receive the mean of the next 2 available ranks (2 and 3, which has mean 2.5), and so the DOOR for both Subject A and Subject D is 2.5. Finally, Subject C has the highest score and therefore receives the worst available rank, which is DOOR=4.

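### SAP 6.5.1 asks whether the outcome visit was held before it reads the medically attended visit records, so a documented pneumonia failure in a child with no visit is set to missing and imputed

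*SAP*

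**What the plan says.** SAP 6.5.1 derives ACR in a fixed order: no recorded dose gives missing, death gives NO, no visit gives missing, and only then are the MAV fields examined. The prose for OAV#1 reads "Otherwise, if a subject does not have OAV#1 then ACR and its components are missing for OAV#1", and the same sentence continues with the matching rule for OAV#2. The OAV#1 pseudocode agrees: "else if subject does not have OAV#1 then ACR_OAV1=missing" is its third branch, ahead of every MAV branch.

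The missing value then passes down the chain. SAP 6.5.5: "Else if the subject has missing ACR at OAV#1 then OCR at OAV#1 will be missing", and this comes before the hospitalisation test that separates OCR 7 from OCR 6. SAP 6.5.7: "DOOR at OAV#1 or at OAV#2 is missing only if OCR or number of days of antibiotic use is missing for the respective OAV".

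SAP 6.5.6 has its own visit rule, "If a subject does not have an OAV#1 or OAV#2, then number of days of antibiotic use at OAV#1 is missing", with an exception under which "subjects that were hospitalized due to pneumonia or a complication of pneumonia or the died during the study period will have number of days" filled in by arm (5 standard, 0 short) when the count is missing.

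SAP 8.4.1 imputes DOOR and OCR by linear regression on site, study treatment, initial antibiotic, age group, ED status, the observed OCR at the other visit, and daily cough and solicited-event grades.

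**The concern.** Failure is defined by an event. Footnote 1 of Table 1 (Protocol 3.2.1, SAP 3.3) asks for a visit or hospitalisation for persistent or worsening pneumonia after at least one dose, and does not require that an OAV was held. Protocol 9.5.2 classes any child needing off-study antimicrobial therapy as an inadequate responder, again without a visit condition. One qualifying MAV in the window therefore already fixes ACR at NO and OCR at 6 or worse. Only the choice between 6 and 7 may stay open.

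Elsewhere the SAP lets a known bad value settle the outcome. In 6.5.3 one positive symptom overrides missing components, and in 6.5.4 one grade 3 event overrides missing days. In 6.5.5, after a failure, "OCR at OAV#1 would still be defined even if most severe solicited event at OAV#1 was missing". A recorded pneumonia failure without an OAV is treated differently.

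The primary intention-to-treat (ITT) DOOR analysis and the ITT OCR analyses, including OCR non-inferiority, would then use a prediction in place of a recorded failure. Failure is the risk that Protocol 2.3.1 names for short course. Protocol 11.4.1 also says that imputation will use DOOR components seen at an early termination visit. The 8.4.1 list has no early-termination ACR, fever or respiratory-rate item, and SAP 13 reports no change to the planned analyses.

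**Working it through.** **Rule walk.** Take a dosed, living child with a qualifying MAV in Day 1 to 5.

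| OAV#1 held | Hospitalised for pneumonia | ACR, OCR as written | ACR, OCR with MAV test first |
|---|---|---|---|
| Yes | No | NO, 6 | NO, 6 |
| Yes | Yes | NO, 7 | NO, 7 |
| No | No | missing, missing | NO, 6 |
| No | Yes | missing, missing | NO, 7 |

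A child with no visit and no recorded failure stays missing under both orders. In the last row the 6.5.6 exception supplies antibiotic days, but DOOR is still missing as written because OCR is missing.

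**What the imputation can see.** If OAV#2 was held, its OCR covers MAVs from Day 1 to 18 and so carries a Day 1 to 5 failure. In the other direction, OCR at OAV#1 covers Day 1 to 5 only and cannot carry a Day 6 to 18 failure. Daily cough and event grades, where recorded, carry some information. There is no direct MAV, hospitalisation, non-study-antibiotic or early-termination ACR item.

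**Scale.** The plan's sample size formula (SAP 5) gives 10.507/(12 × 0.25 × 0.01) = 350.2, against 360 stated, and 360/0.9 = 400, or 200 per arm. It does not depend on this point. The null standard error of the DOOR index, ignoring ties, is √[401/(12 × 200 × 200)] = 0.0289. Each child contributes 1/200 of the index, so replacing one child's value moves it by at most 0.005, and 0.005/0.0289 = 0.17.

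**Simulation.** The documents give no rate of failures without a visit, so every count here is assumed. Assumptions: 200 per arm; 20 imputations; non-failure OCR 1 to 5 at 0.62/0.20/0.05/0.02/0.11 in both arms; failures 80% OCR 6 and 20% OCR 7; antibiotic days 0 in short course (3 if failed) and 5 (90%) or 4 (10%) in standard.

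The shift in the DOOR index when only the hidden failures are missing:

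| Failures short v standard; hidden short + standard | OAV#2 held | Neither visit, three days of grades | Neither visit, no grades |
|---|---|---|---|
| 4 v 4; 1 + 0 | +0.0021 | +0.0027 | +0.0036 |
| 4 v 4; 1 + 1 | +0.0014 | +0.0016 | +0.0021 |
| 8 v 4; 2 + 1 | +0.0032 | +0.0041 | +0.0055 |
| 12 v 5; 6 + 2 (stress) | +0.0102 | +0.0131 | +0.0179 |

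In the first case a recorded OCR of 6 or 7 is imputed on average as 3.2, 3.2 and 1.9. The third row is at most 0.0055/0.0289 = 0.19 of the standard error. It implies three-fold enrichment among 20 short-course non-attenders (2/20 v 6/180); the stress case implies nine-fold (6/20 v 6/180). Equal hiding in both arms still favours short course slightly, because each hidden failure is pulled toward its arm mean. One hidden standard-course failure alone gives -0.0007 (OAV#2 held) to -0.0015 (no information).

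These shifts are not the gain from reordering, because other non-attenders are imputed too. With 20 non-attenders per arm missing and imputation on arm only, the bias against full data is (ranges over repeated runs, Monte Carlo standard error about 0.0005):

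| Case | As written | MAV test first |
|---|---|---|
| 4 v 4; 1 + 0 | +0.003 to +0.004 | -0.001 to 0.000 |
| 4 v 4; 1 + 1 | +0.002 to +0.003 | about 0.000 |
| 8 v 4; 2 + 1 | +0.003 to +0.004 | -0.002 to -0.003 |
| 12 v 5; 6 + 2 (stress) | +0.016 to +0.018 | -0.002 to -0.003 |

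The small over-correction arises because, once failures are coded, the remaining non-attenders are all non-failures but are imputed from a model that includes failures. ACR shows the same in the third case: (8 + 18 × 6/180)/200 - (4 + 19 × 3/180)/200 = 2.14 points, against a true 8/200 - 4/200 = 2.00.

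**Non-inferiority.** With only the hidden failures missing, the OCR index shifts by at most +0.0022 outside the stress case and +0.0084 in it. The lowest OCR lower limit met is 0.482 - 1.96 × 0.0256 = 0.43, above the 0.40 margin.

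**The case against.** Several points on the other side have force.

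- Table 1's column heading places the assessment of ACR at the two OAVs, and Protocol 11.4 leaves to the SAP what counts as sufficient data. So the SAP may set such a rule. That does not explain why a dated, recorded failure is treated as unknown, when death without a visit and failure without event grades are not.
- A reader might infer that recorded failures vanish from the trial. They do not. Table 57 and Listings 13 and 14 show them, and the halting rules in Protocol 9.5.1 count pneumonia failures without a visit condition. In the worst-case analyses a hidden short-course failure is not understated: at OAV#1 a child with OAV#2 held takes the larger of that OCR and 5, and a child with neither visit takes 8. Failing children are also asked to attend both visits (Protocol 4).
- A reader might infer that the imputation is blind to failure. It is not wholly so, since the other visit's OCR and the daily grades carry part of it.
- A reader might infer that 6.5.6 flatly contradicts 6.5.1. The exception still works for deaths and for hospitalised children who attended but lack product records. It is idle only for a hospitalised survivor with no visit.
- The reordering gains little in the 8 v 4 case once all non-attenders are imputed. This stands.

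**Conclusion.** The ordering defect is certain from the text and applies at both visits. Its effect is small on any plausible count. In the cases outside the stress case, the DOOR index moves by a small fraction of its standard error, and the net size depends on how the other non-attenders are imputed. In every simulated case the true DOOR index is 0.68 to 0.71 and no planned conclusion changes.

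A reader might go further and say that the rule biases the primary result toward short course enough to undermine it. The documents do not support that. They give no rate of failures without a visit. The one trial cited for 5 and 10 days (Protocol 2.2) saw no failures in either group, although it was underpowered, and with no failures the rule does nothing.

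This is a minor to moderate point. The case for change is that the rule departs from the endpoint definition and costs little to correct. It does not rest on a demonstrated effect on the result.

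**What to change.** 1. In SAP 6.5.1, for both visits, test for a qualifying MAV in the window before testing whether the visit was held. A documented failure then gives ACR = NO, with OCR 7 if a hospitalisation is recorded in the window and otherwise 6. Keep missing only where there is neither a visit nor a documented failure.
2. In SAP 6.5.6, take these children's antibiotic days from the product-administration and concomitant-medication records even when no visit was held. Otherwise DOOR can stay missing for failures that were not hospitalised. Resolve gaps through the data queries that the section already plans. Do not derive days from the MAV date, because the section limits the sources to those two records; its end-date rule ("If there is a start date but not an end date for a concomitant medication in the clinical database") covers recorded medications only. Do not apply the 0-day default where receipt of a non-study antibiotic is recorded.
3. In SAP 8.4.1, build the completed datasets from all ITT children with a defined DOOR, not from CC-V1 alone. Add the early-termination DOOR components that Protocol 11.4.1 names, coded as the items that attenders have at the visit, or record the departure in SAP 13.
4. Add no visit requirement to the complete-case cohorts. Apply SAP 6.3.2 and 6.5 as written and reconcile them with the early-termination exclusion in 6.3. Also report ACR in the ITT cohort with documented failures counted.

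The cost is SAP wording and programming before unblinding. The MAV, early-termination, withdrawal-call and medication records are already collected. Some failures will remain unrecorded, because health-record review before OAV#1 is done only where feasible (Protocol 7.3). Sample size, power and alpha are unchanged.
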